8.4.4 Lifestyle Restrictions

Participants should not consume ≥ 7 units/week of alcohol during the study. One drink "unit" or one standard drink is equivalent to 12 ounces of beer, 4 ounces of wine, or 1 ounce of hard liquor.

8.4.5 Screen Failures, Retesting, and Rescreening

Screen failures are defined as participants who consent to participate in the clinical study (ie, enroll) but are not subsequently randomized into the study. A minimal set of screen failure information is required to ensure transparent reporting of screen failure participants, to meet the Consolidated Standards of Reporting Trials publishing requirements, and to respond to queries from regulatory authorities. Minimal information includes date of consent, demography, screen failure details, eligibility criteria, and any serious AEs.

Study assessments and/or laboratory parameters (Table 11) may be repeated (retesting) in an effort to find all possible well-qualified participants. Consultation with the medical monitor may be needed to identify whether repeat testing of any particular parameter is clinically relevant. Other than exceptional circumstances, retesting is allowed only once.

Rescreening is allowed but the participant must wait 4 weeks after the date of screen failure to re-enroll. For participants who are rescreened, biopsy, MRE and/or DXA assessments do not need to be repeated if obtained within 8 weeks of randomization. Other than exceptional circumstances, rescreening is allowed only once.

8.4.6 Withdrawal and Replacement of Participants

[figure not shown]
8.4.6.1 Discontinuation of Treatment

Participants MUST discontinue IP (and nonIP at the discretion of the investigator) for any of the following reasons:

• Participant's request to stop study treatment. Participants who request to discontinue study treatment will remain in the study and must continue to be followed for protocol specified follow-up procedures. The only exception to this is when a participant specifically withdraws consent for any further contact with him/her or persons previously authorized by participant to provide this information.

 Any clinical AE, laboratory abnormality or intercurrent illness which, in the opinion of the investigator, indicates that continued participation in the study is not in the best

interest of the participant

- For participants with normal Day 1 (Randomization) liver enzymes and total bilirubin, if there is new elevation of ALT or AST > 3 × ULN, repeat testing should be performed within 48 to 72 hours. If elevation persists, then standard drug-induced liver injury (DILI) discontinuation criteria will be applied and study treatment will be discontinued if any of the following occur:
 - \circ ALT or AST $> 8 \times ULN$
 - \circ ALT or AST $> 5 \times$ ULN for more than 2 weeks
 - \circ ALT or AST $> 3 \times$ ULN and (total bilirubin $> 2 \times$ ULN or INR > 1.5)
 - o ALT or AST $> 3 \times$ ULN with the appearance of fatigue, nausea, vomiting, right upper quadrant pain or tenderness, fever, rash, and/or eosinophilia (> 5%)

Note: If participant lives in a remote location, a local laboratory may be used for repeat testing, and results should be promptly communicated to the site. Participants meeting the criteria above may have potential DILI, see Section 8.6.2.1.7 for reporting requirements

- For participants with elevated AST, ALT, or total bilirubin at Day 1 (Randomization), if there is new elevation of ALT or AST > 2 × ULN or total bilirubin 1.5 × Day 1 bilirubin, repeat testing should be performed within 48 to 72 hours. If elevation persists, then study treatment will be discontinued if any of the following occur:
 - \circ ALT or AST levels increase to $> 5 \times \text{Day 1}$ (Randomization) measurement
 - ALT or AST levels increase > 2 × Day 1 (Randomization) measurements AND the increase is accompanied by a concomitant increase in total bilirubin to > 2 × Day 1 bilirubin or the INR concomitantly increases by > 0.3
 - o Appearance of fatigue, nausea, vomiting, right upper quadrant pain or tenderness, fever, rash, and/or eosinophilia (> 5%)

Note: If participant lives in a remote location, a local laboratory may be used for repeat testing, and results should be promptly communicated to the site. Participants meeting the criteria above may have potential DILI, see Section 8.6.2.1.7 for reporting requirements

- Termination of the study by BMS
- Loss of ability to freely provide consent through imprisonment or involuntary incarceration for treatment of either a psychiatric or physical (eg, infectious disease) illness
- Abnormal liver tests suggestive of liver injury, as defined in Section 8.6.2.1.7, or hepatic decompensation
- Any significant protocol violation (eg, demonstrated lack of treatment compliance). The violation should be discussed with the medical monitor prior to discontinuing the participant. Waivers for protocol violations will not be provided by the sponsor or the medical monitor.
- The investigator feels that it is no longer in the participant's best interest to continue study treatment.
- The participant becomes pregnant (study treatment must be discontinued immediately): In the case of pregnancy (Section 8.6.2.1.5), the investigator must immediately notify the medical monitor or designee of this event. In the event a female participant becomes

pregnant during a clinical trial, the study treatment must be discontinued immediately. In most cases, the study treatment will be permanently discontinued in an appropriate manner (eg, dose tapering if necessary for participant safety). Please contact the medical monitor or designee within 24 hours of awareness of the pregnancy.

See the Schedule of Activities (Section 1.2) for details on the data to be collected at the time of treatment discontinuation and follow-up and any further evaluations that need to be completed.

All participants who discontinue study treatment should comply with protocol-specified follow-up procedures as outlined in Section 1.2. The only exception to this requirement is when a participant withdraws consent for all study procedures including post-treatment study follow-up or loses the ability to consent freely (ie, is imprisoned or involuntarily incarcerated for the treatment of either a psychiatric or physical illness). Participants are not to be replaced.

If study treatment is discontinued prior to the participant's completion of the study, the reason for the discontinuation must be documented in the participant's medical records and entered on the appropriate electronic case report form (eCRF) page. As indicated, appropriate follow-up and/or alternate medical care must be arranged for the participant.

Participants who discontinue study treatment will remain in the study for continued follow-up.

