otherwise noted)		W 1	W 2	W 3	W 4	W 5	W 6		W 7	W 8	W 9	W 10	W 11	W 12	
Pharmacokinet	ic 🔼			San	npling	,									
Blood PK sampling	X	X	X		X	X	X	X	X	X			X	X	 See Section 8.6.3 and Table 12. *Day 4 and Day 46: Postinfusion: Sample may be collected ± 1 day at the PK visit. Day 15, Day 36, Day 50, and Day 57: Pre-infusion: Samples may be collected up to 120 minutes prior to the start of the infusion. Day 85: Collect sample 1 week after last administration. Day 8, Day 29, Day 43, and Day 78: Samples should be collected at: Pre-infusion: Samples may be collected up to 120 minutes prior to the start of the infusion. Mid-infusion: Samples should be collected ± 3 minutes within specified timeframe. If infusion is administered at a modified rate, the timing of collection of this sample should correspond to the middle of the modified infusion duration of the total administered dose. End-of-infusion: Samples should be collected 2 minutes within specified timeframe. This sample should be taken immediately prior to stopping the infusion. If the end of infusion is delayed to beyond the nominal infusion duration, the collection of this sample should also be delayed accordingly. Postinfusion: Samples should be collected 1 hour ± 3 minutes postinfusion.

Table 2 On-Treatment Procedural Outline IM025006: Part 1, Treatment Period (Day 4 through Day 85)

Procedure/Vi sit Day				12-	week,	, Doub	ole-Bl	ind, T	reatmo	ent Pe	eriod				Notes
(± 3 days for all visits unless	D 4ª	D 8	D 15	D 22	D 29	D 36	D 43	D 46 ^a	D 50	D 57	D 64	D 71	D 78	D 85	
otherwise noted)		W 1	W 2	W 3	W 4	W 5	W 6		W 7	W 8	W 9	W 10	W 11	W 12	

Table 2 On-Treatment Procedural Outline IM025006: Part 1, Treatment Period (Day 4 through Day 85)

Procedure/Vi sit Day				12-	-week,	, Doub	ole-Bl	ind, Tı	reatmo	ent Pe	eriod				Notes
(± 3 days for all visits unless	D 4ª	D 8	D 15	D 22	D 29	D 36	D 43	D 46 ^a	D 50	D 57	D 64	D 71	D 78	D 85	
otherwise noted)		W 1	W 2	W 3	W 4	W 5	W 6		W 7	W 8	W 9	W 10	W 11	W 12	

Table 2 On-Treatment Procedural Outline IM025006: Part 1, Treatment Period (Day 4 through Day 85)

Procedure/Vi sit Day	_			12-	-week	, Doub	ole-Bl	ind, T	reatm	ent Po	eriod				Notes
(± 3 days for all visits unless	D 4ª	D 8	D 15	D 22	D 29	D 36	D 43	D 46 ^a	D 50	D 57	D 64	D 71	D 78	D 85	
otherwise noted)		W 1	W 2	W 3	W 4	W 5	W 6		W 7	W 8	W 9	W 10	W 11	W 12	

On-Treatment Procedural Outline IM025006: Part 1, Treatment Period (Day 4 through Day 85) Table 2

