 - b) Participants taking anti-obesity agents (eg, ORLISTAT®) within 4 weeks of the first dose of study treatment.
 - c) Participants receiving interferon therapy for any disease, or received interferon therapy for any disease within 52 weeks prior to administration of study treatment.
 - d) The participant takes any vitamin A containing supplements or multivitamins, or vitamin A containing medications after signing the ICF.
 - e) Participants taking anti-diabetic or anti-dyslipidemic medication receiving stable doses for less than 30 days prior to the first dose of study medication.
 - f) Participants unable to comply with restrictions and prohibited treatments.
 - g) Participants who have not discontinued other investigational agents must be discontinued at least 12 weeks or 5 half-lives before the first dose of study treatment, whichever is longer.
 - h) Prior exposure to BMS-986263
 - i) The participant has received recent treatment with alternative therapies, which, in the opinion of the investigator, could potentially confound clinical or laboratory assessments (eg, herbal supplements).
- 4. Physical and laboratory test findings
 - a) Evidence of organ dysfunction or any clinically significant deviation from normal in physical examination, vital signs, ECG, or clinical laboratory determinations beyond what is consistent with the target population
 - b) Body mass index (BMI) > 34 kg/m^2 . Participants with a BMI of $30\text{-}34 \text{ kg/m}^2$ must have an ALT \leq upper limit of the normal range (ULN).

- c) The participant's baseline laboratory test results include abnormal values considered to be clinically significant by the investigator.
- d) The participant's laboratory test results at screening include any of the following:
 - albumin < 3.5 g/dL
 - INR > ULN
 - ALT value $> 2 \times$ the ULN
 - hemoglobin A1c \geq 9.0%
 - total bilirubin > ULN
 - hemoglobin < lower limit of normal (LLN)
 - platelet count $< 100,000/\mu L$
 - white blood cell count $\leq 3000/\mu L$
- e) Glomerular filtration rate < 30 mL/min/1.73 m² according to the Modification of Diet in Renal Disease equation.
- f) The participant's vitamin A levels at screening are > ULN
- g) Alpha-fetoprotein (AFP; see Exclusion 1e, above):
 - i. AFP > 100 ng/mL (> 82.6 IU/mL) OR
 - ii. AFP ≥ 50 and ≤ 100 ng/mL (≥ 41.3 IU/mL and ≤ 82.6 IU/mL) with liver ultrasound showing findings suspicious for HCC.
- 5. Not applicable.
- 6. Allergies and adverse drug reaction

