8.6.2.1.7 Potential Liver Injury

Wherever possible, timely confirmation of initial liver-related laboratory abnormalities should occur prior to the reporting of a potential DILI event. The study treatment discontinuation criteria are provided in Section 8.4.6.1. All occurrences of potential DILIs, meeting the defined criteria, must be reported as SAEs (Appendix 2 for reporting details).

Participants who meet criteria for DILI should have relevant laboratory testing (eg, ALT, AST, and INR levels) repeated at least weekly until abnormalities have resolved. Tests should be repeated within 3 days; then, every 3 days until reversal is noted; and then, every week until normalization. The investigator should make every effort to determine if any other cause for the liver test abnormalities is present.

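### The stopping list for participants with elevated Day 1 liver tests has no sustained-elevation rule, so a lasting isolated rise between 5 × ULN and 5 × Day 1 meets no numeric stop

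*Protocol*

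**What the plan says.** Protocol 8.4.6.1 divides participants by their Day 1 liver tests.

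- **Normal Day 1 tests.** A new ALT or AST above 3 × ULN is retested within 48–72 hours. If it persists, treatment stops at any of: above 8 × ULN; above 5 × "ULN for more than 2 weeks"; above 3 × ULN with bilirubin above 2 × ULN or INR above 1.5; above 3 × ULN with listed symptoms or eosinophilia.
- **Elevated Day 1 tests.** The list opens "For participants with elevated AST, ALT, or total bilirubin at Day 1 (Randomization), if there is new elevation of ALT or AST" above 2 × ULN, or bilirubin at 1.5 × Day 1, with the same retest. Treatment then stops at any of: ALT or AST above 5 × Day 1; "ALT or AST levels increase > 2 × Day 1 (Randomization) measurements AND the increase is accompanied by a concomitant increase in total bilirubin" to above 2 × Day 1, or by an INR rise above 0.3; appearance of the listed symptoms or eosinophilia.

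A further reason for stopping applies to everyone: "Abnormal liver tests suggestive of liver injury, as defined in Section 8.6.2.1.7, or hepatic decompensation". Section 8.6.2.1.7 supplies no threshold of its own and says "The study treatment discontinuation criteria are provided in Section 8.4.6.1". It also requires potential DILI meeting the defined criteria to be reported as an SAE, and sets a repeat-testing schedule for participants who meet them. Appendix 2 takes its definition of potential DILI from 8.4.6.1.

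**The concern.** Four rules face three, and the one without a match is the rule with a time element. A participant with normal Day 1 tests whose ALT stays at 6 × ULN for three weeks must stop. A participant who began at 1.5 × ULN and does the same meets no number in the plan. The bullet on abnormal liver tests does not settle it, because 8.4.6.1 and 8.6.2.1.7 refer to each other.

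What is at stake is continued dosing on judgement alone in METAVIR Stage 3 or 4 participants, where the other group has a mandatory stop. Reporting is affected too. An episode that meets no criterion in 8.4.6.1 is not potential DILI by definition, so neither SAE reporting nor the repeat-testing schedule starts automatically. Section 8.2 names SAEs as part of the external DMC's safety review.

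**Working it through.** **1. The baseline-relative stop on the ULN scale.** Write b for the Day 1 value of the enzyme divided by ULN. The enzyme-alone stop is then 5 × b. The range with no numeric stop runs from 5 to 5 × b, and exists only when b is above 1.

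| Day 1 (× ULN) | 5 × Day 1 (× ULN) | Range with no numeric stop (× ULN) |
|---|---|---|
| 1.0 | 5.0 | none |
| 1.2 | 6.0 | 5–6 |
| 1.5 | 7.5 | 5–7.5 |
| 1.6 | 8.0 | 5–8 |
| 2.0 | 10.0 | 5–10 |

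At b = 1.6 the limit equals the immediate 8 × ULN stop of the normal-baseline list (5 × 1.6 = 8). Above that, the range passes it. The range presumes no listed symptom, no eosinophilia above 5%, no bilirubin above 2 × Day 1 and no INR rise above 0.3.

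**2. Where the elevated-baseline list is stricter.**

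- Retesting starts at 2 × ULN instead of 3 × ULN.
- The enzyme-alone limit is below 8 × ULN when b is below 1.6.
- The joint enzyme limit, 2 × b, is below 3 × ULN when b is below 1.5.
- Day 1 INR + 0.3 is below 1.5 when Day 1 INR is below 1.2.
- The symptom stop has no 3 × ULN floor.

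**3. Who can have b above 1.** Exclusion 4d in 8.4.2 ("The participant's laboratory test results at screening include any of the following") removes ALT above 2 × ULN; the synopsis prints at or above 2 × ULN. It also removes bilirubin above ULN and lists no AST limit. These limits apply at screening. Day 1 chemistry is drawn at least 2 weeks apart from it (8.1.1) and has no stated cap, so 2.0 × ULN is an illustration and not a maximum. Exclusion 4b requires ALT at or below ULN at BMI 30–34 and excludes BMI above 34, so raised screening ALT is possible only below BMI 30. Exclusions 4a and 4c remove abnormalities judged clinically significant.

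**4. Upper bounds on infusions while the value stays in the range.** Onset days are assumptions. Part 1 infusions fall on Days 1, 8, …, 78, which is 12; for the end of dosing Table 2 gives "Day 85: Collect sample 1 week after last administration". Chemistry is weekly. Part 2 infusions fall on Days 1, 15, …, 155, which is also 12. Chemistry is weekly to Day 85, then every 2 weeks from Day 99 to Day 169.

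| Setting and onset | First scheduled draw more than 14 days later | Infusions under the normal-baseline rule | Infusions if nothing else stops treatment |
|---|---|---|---|
| Part 1, Day 8 | Day 29 | 3 (4 if Day 29 is infused before the result) | 11 |
| Part 1, Day 43 | Day 64 | 3–4 | 6 |
| Part 1, Day 57 | Day 78 | 3–4 | 4 |
| Part 2 Q2W active, Day 15 | Day 36 | 2 | 11 |
| Part 2 Q2W active, Day 43 | Day 64 | 2 | 9 |
| Part 2 Q2W active, Day 85 | Day 113 | 2–3 | 6 |

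The Q4W arm is omitted because 6 of its 11 infusions from Day 15 to Day 155 are placebo (footnote to Table 8). The last column is a ceiling: it assumes no symptom, no interruption and no judgement stop throughout.

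**The case against.** The strongest reply is that the sponsor chose one baseline-scaled limit, without a waiting time, to do the work of both enzyme-alone rules. At Day 1 1.2 × ULN a rise to 6–8 × ULN stops at once, where a normal-baseline participant waits more than 2 weeks. That range is 2 × ULN wide, against 1 × ULN (5–6) of lesser protection. This stands as a defence of baseline multiples, but it weakens as Day 1 rises. At 1.5 × ULN the stricter range is 0.5 wide (7.5–8) and the looser one 2.5 wide (5–7.5). From 1.6 × ULN there is no stricter range for an enzyme rise alone.

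It is also fair that several protections remain. The judgement reasons stand under the heading of mandatory discontinuation, 8.5.5 provides for interruption because of an AE, fatigue or nausea alone can trigger the symptom stop, and investigators must document their laboratory review. The infusion ceilings therefore overstate what is likely, and the Part 2 rows concern a part that 8.3 allows may not start. All of this stands and limits the weight of the point. None of it supplies a numeric or duration rule, and the retest leads back to the same three stops.

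A reader might infer that the two lists contradict each other, that participants with elevated tests are unprotected, or that their list is laxer throughout. The documents support none of these: the lists cover separate groups, judgement stops apply to both, and the second list is stricter in the respects shown above.

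**Conclusion.** The gap is real and narrow. For an enzyme above ULN on Day 1, a sustained, isolated, asymptomatic rise between 5 × ULN and 5 × Day 1 is a mandatory stop in one group and a matter of judgement in the other, and it falls outside the automatic potential-DILI reporting and retesting. The range is 1 × ULN wide at Day 1 1.2 × ULN, 2.5 wide at 1.5 × and 5 wide at 2.0 ×. Above 1.6 × ULN, values over 8 × ULN are included. For an enzyme at or below ULN on Day 1 there is no gap.

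It would be tempting to say how many participants are affected, or to treat 11 infusions as expected exposure. The documents give no rate of raised Day 1 enzymes or of sustained values above 5 × ULN, so neither can be claimed. This is an improvement worth considering, held with medium confidence because redacted safety text and the DMC charter could not be checked.

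**What to change.** Add one bullet to the elevated-baseline list in 8.4.6.1: *ALT or AST > 5 × ULN and > 2 × Day 1 measurement for more than 2 weeks*. Because potential DILI is defined by that section, the bullet also brings such episodes under SAE reporting and repeat testing.

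The acting threshold is the larger of 5 × ULN and 2 × Day 1. The guard has no effect up to Day 1 2.5 × ULN (2 × 2.5 = 5). Above that it prevents a stop on a small rise: at Day 1 AST 4 × ULN the bullet acts above 8 × ULN, a 2-fold rise, instead of above 5 × ULN, a 1.25-fold rise. The documents do not supply this guard, so the sponsor's medical team should confirm it. They should also decide whether participants above Day 1 1.6 × ULN need an immediate 8 × ULN stop, which the bullet does not restore. If the omission was deliberate, one sentence of rationale would do.

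No new tests are needed. The downside is possibly a few more treatment discontinuations. In Part 2, Section 9.1 counts early discontinuation as nonresponse, so each extra stop costs at most one responder in about 30 in its arm (1/30 = 3.3 percentage points). Section 8.4.6.4 lets the sponsor enrol more participants if dropout is high. In Part 1 the loss should be smaller: SAP 9.5.1 counts nonresponse only when the Week 12 measurement is missing, and participants who stop treatment remain in follow-up.

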8.4.6.2 Discontinuation from the Study

Participants who request to discontinue study treatment will remain in the study and will continue to be followed for protocol specified follow-up procedures. The only exception to this is when a participant specifically withdraws consent for any further contact with him/her or persons previously authorized by participant to provide this information. Expectations are as follows:

- Participants should notify the investigator of the decision to withdraw consent from future follow-up in writing, whenever possible.
- The withdrawal of consent should be explained in detail in the medical records by the investigator, as to whether the withdrawal is from further treatment with study treatment only or also from study procedures and/or post treatment study follow-up, and entered on the appropriate eCRF page.
- In the event that vital status (whether the participant is alive or dead) is being measured, publicly available information should be used to determine vital status only as appropriately directed in accordance with local law.
- If the participant withdraws consent for disclosure of future information, the sponsor may retain and continue to use any data collected before such a withdrawal of consent.
- Assessments for the end of treatment/end of study visit must be performed, provided that the participant has not withdrawn consent for these activities.
- All required eCRF pages must be completed, including the date of and explanation for the withdrawal.
- As indicated, appropriate follow-up and/or alternate medical care must be arranged for the participant.

8.4.6.3 Lost to Follow-up

• All reasonable efforts must be made to locate participants to determine and report their ongoing status. This includes follow-up with persons authorized by the participant.

- Lost to follow-up is defined by the inability to reach the participant after a minimum of 3 documented phone calls, faxes, or emails as well as lack of response by participant to one registered mail letter. All attempts should be documented in the participant's medical records.
- If it is determined that the participant has died, the site will use permissible local methods to obtain date and cause of death.
- If investigator's use of third-party representative to assist in the follow-up portion of the study has been included in the participant's informed consent, then the investigator may use a sponsor retained third-party representative to assist site staff with obtaining participant's contact information or other public vital status data necessary to complete the follow-up portion of the study.
- The site staff and representative will consult publicly available sources, such as public health registries and databases, in order to obtain updated contact information.
- If after all attempts, the participant remains lost to follow-up, then the last known alive date as determined by the investigator should be reported and documented in the participant's medical records.

